8.8.2.3 Time to First BM

For the time to first BM endpoint, the distribution for each treatment arm will be estimated by the Kaplan-Meier method and will be compared by the Log-rank test. The median time along with the 95% confidence

limits for the median will be presented for each treatment arm. Simultaneous confidence bounds for the Kaplan-Meier curve will be computed for all treatment groups.

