5. STATISTICAL METHODS

Seven treatment groups are identified for all analyses cited in the following as “by treatment group”: subjects in Age Group A receiving plecanatide doses of 0.5 mg, 1.0 mg, or placebo; subjects in Age Group B receiving plecanatide doses of 1.0 mg, 2.0 mg, 3.0 mg, or placebo. Following comparisons will be included:

1) For Age Group A:

Age: 6 to 11 years				
0.5 mg	1.0 mg	Active Doses Combined	Placebo	

2) For Age Group B:

Age: 12 to < 18 years				
1.0 mg	2.0 mg	3.0 mg	Active Doses Combined	Placebo

3) Overall:

Overall	
Plecanatide	Placebo

Descriptive statistical methods will be used to summarize the data from this study, with hypothesis testing performed for the primary and secondary efficacy endpoints. Unless stated otherwise, the term “descriptive statistics” refers to number of subjects (n), mean, median, standard deviation (SD), minimum and maximum for continuous data and frequencies and percentages for categorical data. Unless otherwise

noted, percentages will be calculated using the total number of subjects in the appropriate population and/or subgroup and per treatment group where applicable. Where data are collected over time, both the observed data and change from the Screening Period (baseline) will be summarized at each time point.

Statistical testing including p-values and confidence intervals (CIs) will be presented as described in each section below. The Type I error rate (alpha) for the analysis of the primary efficacy endpoint is 0.05 (two-sided).

Where applicable, comparisons among treatment groups will be performed using an analysis of variance/covariance (ANOVA/ANCOVA) model for continuous variables and a Cochran-Mantel-Haenszel (CMH) test for categorical variables.

For all repeated measures efficacy analyses, the following covariance structures will be examined: compound symmetry, first order autoregressive, and unstructured. The covariance structure with the best model fit will be selected for each efficacy endpoint.

All data collected during the study will be included in data listings. Unless otherwise noted, the data will be sorted first by treatment group, subject number, and then by date within each subject number.

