5.2.4.3. Time to First BM

For the time to first BM endpoint, the distribution for each treatment group within each age group, combined active doses within age group, and overall active doses will be estimated by the Kaplan-Meier method and will be compared by the Log-rank test. The median and quartile time along with the 95% confidence limits for the median will be presented for each treatment group.

Kaplan-Meier curves with 95% confidence limits will also be presented graphically by treatment group (Age group A and B with Placebo on one page, and Combined age group with Placebo on a second page).

The above analysis will be repeated for the PP Population.

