5.2.4.5. Use of Rescue Medication

The proportion of subjects who used at least one dose of rescue medication during the treatment period, will be summarized by treatment group. The number of tablets of rescue medication used per week, and overall, for the 4-week treatment period will be analyzed by treatment group. The Mann Whitney U Test (Wilcoxon Rank Sum Test) will be used to compare the difference between each treatment group, combined active doses within each age group, and overall active doses, versus Placebo at each week, and over all 4 weeks, of the 4-week treatment period.

The above analysis will be repeated for the PP Population.

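### The overall log-rank test for time to first BM should be stratified by age group, because allocation differs by age, and SAP 5.2.4.3 should name its placebo contrasts

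*Combined protocol and SAP*

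**What the plan says.** SAP 5.2.4.3 estimates Kaplan-Meier curves for "the distribution for each treatment group within each age group", and continues: "combined active doses within age group, and overall active doses will be estimated by the Kaplan-Meier method and will be compared by the Log-rank test". It does not say against what, whether the tests are pairwise or global, or whether they are stratified. Protocol 8.8.2.3 is equally brief: "the distribution for each treatment arm will be estimated by the Kaplan-Meier method and will be compared by the Log-rank test".

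The neighbouring SAP 5.2.4.5 uses almost the same list of groups and completes it: "compare the difference between each treatment group, combined active doses within each age group, and overall active doses, versus Placebo". The remaining parts of SAP 5.2.4 also name placebo.

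SAP section 5 supplies a general scheme. After the words "Following comparisons will be included" it sets out three blocks: Age Group A with its doses, combined active and placebo; Age Group B likewise; and Overall, plecanatide and placebo. SAP 3.3.1 states that enrolment is stratified by age group and randomisation by gender. SAP 3.2 gives 1:1:1 allocation in Group A and 1:1:1:1 in Group B.

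**The concern.** The overall comparison pools two age groups that were randomised in different ratios. Randomisation protects the comparison within each age group. It does not make pooled active and pooled placebo alike in age. If children and adolescents differ in how soon they have a first BM, part of that difference enters the overall drug comparison unless the test is stratified by age group.

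Two things are at stake. The overall result is shifted in a direction set by the age effect, not by the drug. The test also loses sensitivity, because a prognostic factor already used in the design is ignored. Separately, leaving the contrasts unnamed lets two programmers produce different p-values from the same sentence, for example one omnibus test across the arms of an age group or a set of comparisons with placebo.

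**Working it through.** **No plan figure to reproduce.** The documents state no power or hazard ratio for this endpoint. Their one power figure concerns weekly SBM frequency and does not bear on this point.

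**Inputs from the documents.** There are 30 patients in each of seven age/dose groups (SAP 3.2).
- Group A: 60 active, 30 placebo (2:1).
- Group B: 90 active, 30 placebo (3:1).
- Overall: 150 active, 60 placebo.

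**Age imbalance built into the pooled groups.**
- Children among active: 60/150 = 40%.
- Children among placebo: 30/60 = 50%.
- Adolescents are therefore 60% of active and 50% of placebo patients, a difference of 0.10.

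**Assumptions not in the documents.** Times are exponential and censored at Day 28. The age hazard ratio is 1.5 or 2.0, with adolescents slower unless stated. The drug hazard ratio is 1.6 at every dose. The test is two-sided at 0.05, the level that the SAP states for the primary endpoint.

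**Size of the shift, by hand.** Suppose nearly every patient has a first BM by Day 28. The variance term of the unstratified log-rank test is then about 210 × (150/210) × (60/210) = 42.9, with square root 6.55. With no drug effect, the pooled log hazard ratio is displaced by roughly 0.10 × ln(age HR):
- Age HR 1.5: 0.10 × 0.405 = 0.041, so Z shifts by about 0.041 × 6.55 = 0.27.
- Age HR 2.0: 0.10 × 0.693 = 0.069, so Z shifts by about 0.069 × 6.55 = 0.45.

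Simulation at the planned size gives mean null Z of about −0.29 and −0.38. This agrees with the hand calculation to within its accuracy. The sign is against plecanatide when adolescents are slower, and reverses when they are faster.

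**Type I error.** With no drug effect and an adolescent-to-child hazard ratio from 1.0 to 3.0, 5,000 runs per scenario gave rejection rates of 4.8 to 6.4% unstratified and 4.8 to 5.4% stratified by age group. The Monte Carlo standard error is about 0.3 points. Tests within Group A or within Group B stayed at 5.4 to 6.5% whatever the age effect.

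**Power of the overall test at drug HR 1.6, adolescents slower.** The ranges cover separate simulations.

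| Age HR | Unstratified | Stratified by age group |
|---|---|---|
| 1.5 | 75–77% | 83–85% |
| 2.0 | 66–68% | 84–85% |

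**Cross-check of the stratified figure.** The stratum variance terms are 90 × (2/3) × (1/3) = 20 and 120 × (3/4) × (1/4) = 22.5, total 42.5, with square root 6.52. Expected Z is ln(1.6) × 6.52 = 0.470 × 6.52 = 3.06. Power is about Φ(3.06 − 1.96) = 86%, close to the simulated value.

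**Where the loss comes from.** Taking only the 0.27 shift off, Φ(3.06 − 0.27 − 1.96) = Φ(0.83) = 80%. The simulated 75–77% is lower because ignoring age also dilutes the drug hazard ratio. The loss therefore has two sources, the shift and the dilution, and stratification addresses both.

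**The case against.** A reader might infer that, as written, one log-rank test compares all seven age/dose curves, so that it could reject merely because children differ from adolescents. The documents do not support this. SAP section 5 lists three separate sets, each with placebo. SAP 5.2.4.3 says within each age group. The table and figure shells for this endpoint are per age group. The listed groups also overlap, since combined active contains the single doses, so they cannot all enter one test. The figure instruction, "Age group A and B with Placebo on one page, and Combined age group with Placebo on a second page", concerns page layout and does not define a test. The protocol's wording about each arm, and its grouping with a single pooled placebo in 8.4, give way to the SAP for secondary analyses (protocol section 8).

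It can also be said that the missing comparator is mostly detail that SAP section 5 and the sister sections would settle; that omitting a balanced factor such as gender does not invalidate a log-rank test; that the rescue-medication Wilcoxon test is unstratified too; and that the overall mixed models do not list age group either. All of this stands. It makes the contrast wording a clarification and gender stratification a matter of consistency with the mixed models, which do include gender. It does not answer the age imbalance in the overall test, because age group, unlike gender, is unbalanced between pooled active and pooled placebo by design.

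**Conclusion.** The point holds as an omission with one substantive consequence. The overall active-versus-placebo log-rank test is unstratified although allocation differs by age group. Its result is shifted by any age difference, and it has roughly 8 to 18 points less power than the age-stratified test under the assumptions above with adolescents slower. If adolescents are faster, the shift favours plecanatide, so any gain in rejections would partly reflect age.

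Inflated false-positive error is a tempting further inference, but the calculations do not bear it out: type I error stays near 5 to 7%. The within-age comparisons are unaffected by age.

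The power figures rest on assumed exponential times, an assumed common drug effect at all doses and assumed age hazard ratios. With no age difference, the two overall tests would perform almost alike. Only the 40% versus 50% imbalance comes directly from the documents. Severity is minor: this is one secondary endpoint in a phase 2 trial declared exploratory, with no multiplicity adjustment.

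**What to change.** In SAP 5.2.4.3, replace the comparison wording with:

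*Within each age group, each dose and the combined active doses will each be compared with that age group's placebo by a log-rank test stratified by gender. Overall active versus placebo will be compared by a log-rank test stratified by age group and gender.*

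Plot each age group's curves with its own placebo curve, in line with the per-age-group figure shells. The change should be made before unblinding. It costs one SAP edit and a strata statement in the program. It needs no new data, and both factors are already recorded for every randomised patient. Spelling out the pairwise contrasts may add a few p-values to an endpoint already treated as exploratory.

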19. Patient reports having more than 1 loose, mushy stool (Diary-recorded stool consistency of 6 on the Bristol Stool Form Scale (BSFS or 4 on the modified Bristol Stool Form Scale for Children [mBSFS-C]) or any watery stool (Diary-recorded stool consistency of 7 on the BSFS or 5 on the mBSFS-C) with any SBM that occurred in the absence of laxative use on the calendar day of the BM or the calendar day before the BM during each 7-day (week) period before the randomization day and up to the day of randomization;
20. ≥ 3 CSBMs per week for either week of the 2-week baseline diary assessment immediately preceding the randomization visit;
21. > 6 SBMs per week for either week of the 2-week baseline diary assessment immediately preceding the randomization visit;
22. Patient reports worst abdominal pain intensity (WAPI) scores in the 2-week baseline diary that meet either of the following:
 - a. WAPI score of 0 on the 11-point Numeric Rating Scale or Wong-Baker Faces® Pain Rating Scale for more than two days during each week of the 2-week baseline diary period.
 - b. An average WAPI < 3 for either of the two weeks of the baseline diary;

23. Completion of < 5 of the 7 required daily diary entries in each week of the 2-week baseline diary assessment immediately preceding the randomization visit;
24. Use of rescue medication (Dulcolax®, bisacodyl) for more than 2 days during either of the two weeks of the 2-week baseline diary assessment immediately preceding the randomization visit.

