3.2. RANDOMIZATION AND MASKING

This is a double-blind, placebo-controlled study with seven treatment age/dose groups that will be conducted at up to approximately 20 clinical sites. Subjects 6-11 years of age will be randomly assigned to 1 of 3 treatment groups (2 active treatments, 1 matching placebo) in a 1:1:1 ratio stratified by gender and subjects 12 to < 18 years of age will be randomly assigned to 1 of 4 treatment groups (3 active treatments, 1 matching placebo) in a 1:1:1:1 ratio stratified by gender using an Interactive Web-based Response System (IWRS).

Central, block randomization will be performed with stratification by gender.

Age Dose Group		Treatment		No. of Tablets to be Taken Daily	Dose Level	Number of Subjects
A	6 to 11 yrs. old	1	0.5 mg plecanatide	1	0.5 mg plecanatide	30
A	6 to 11 yrs. old	2	1.0 mg plecanatide	1	1.0 mg plecanatide	30

A	6 to 11 yrs. old	3	Matching placebo	1	placebo	30
B	12 to < 18 yrs. old	4	0.5 mg plecanatide	2	1.0 mg plecanatide	30
B	12 to < 18 yrs. old	5	1.0 mg plecanatide	2	2.0 mg plecanatide	30
B	12 to < 18 yrs. old	6	1.5 mg plecanatide	2	3.0 mg plecanatide	30
B	12 to < 18 yrs. old	7	Matching placebo	2	placebo	30

The study will be performed in a double-blind manner. All study drugs will be supplied in identical blister packs and tablets will be similar in color, smell, taste, and appearance, thereby assuring double-blind conditions.

The gender-stratified randomization schedule was prepared by Foehl Statistics & Analytics LLC.

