3.3. HANDLING OF DATA

3.3.1. Strata and Covariates

Enrollment will be stratified by age group (6 to 11 years and 12 to < 18 years). Randomization will be stratified by gender to ensure gender balance across treatment groups.

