3.3.7. Definitions and Terminology

Age

The age of a subject is defined as the number of whole years between the subject's birth date and the date of screening. If a subject is anticipated to turn 12 between screening and randomization, he/she will be randomized into the adolescent group but will use the Wong Baker and the mBSFS. A subject who turns 12 during the treatment period or post-treatment follow-up period will remain in 6 to 11 years age group and will use the Wong Baker and the mBSFS. The questionnaires will be provided based on the age at Screening.

All subjects in 6 to 11 years old age group are expected to get the parental oversight on eDiary records. All subjects in 12 to <18 years old age group can complete eDiary by themselves but should be discussed with parent.

Baseline Value

For purposes of safety analysis, the baseline value is defined as the last non-missing value obtained prior to the randomization.

For purposes of efficacy analysis, the baseline values will be derived from data collected in the 2-week electronic diary assessment at the end of the Screening Period (baseline). The last 14 days of diary entries prior to Day 1 will be the default standard for derivation of these values.

The baseline BM (SBM, CSBM) weekly rate will be the weekly average number of BMs (SBMs, CSBMs) recorded during the 2-week baseline assessment period; similarly, for frequency of abdominal pain and abdominal discomfort, frequency of fecal incontinence, frequency of defecation pain, and frequency of large diameter stools. Baseline stool consistency, severity of abdominal pain, abdominal discomfort, and severity of defecation pain will be calculated as follows: for each week of the baseline assessment, the weekly average is the sum of the non-missing scores recorded during the week divided by the total number of non-missing scores recorded during that week; the baseline is then equal to the average of the 2 weekly average scores defined as sum of the 2 weekly average scores divided by 2.

Day 1 (Baseline)

Day 1 is the earliest day that study drug is initiated.

Study Day

Study Day is defined relative to Baseline (Day 1). Thus, the study day of an event is calculated as:

Study Day = Event Start Date – Baseline Date + 1, for dates on or after Day 1;

Study Day = Event Start Date – Baseline Date, for dates before Day 1.

Study Visit

Study Visit is the nominal visit as recorded on the CRF.

Change from Baseline

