5.2.4.2. Change from Baseline in Frequency of BMs and CSBMs, by Study Week

The weekly BM (and CSBM) rate for each subject will be computed, as described in [Section 3.3.7](#), for each week of the 4-week treatment period and for the two weeks of the follow-up period. A summary, by treatment group, of the mean weekly BM (and CSBM) rate and change from baseline in mean weekly BM (and CSBM) rate, for each of the 6 study weeks will be presented. The change from baseline in mean weekly BM (and CSBM) rate will be analyzed using a linear mixed-effects ANCOVA model with fixed effects for gender (stratification variable), treatment, week, the interaction of treatment and week, and the corresponding baseline value; a random intercept for subject will also be specified. The least squares (LS) mean change from baseline will be presented, by treatment groups, and the difference in LS means for each treatment group versus placebo and combined active doses within each age group versus placebo in a separate model for each age group, and overall active doses versus placebo in a separate model with 95% confidence intervals and corresponding statistical p-values.

The baseline BM (and CSBM) rate will be calculated as the average BM (and CSBM) rate for each of the two weeks preceding initiation of study drug.

The above analysis will be repeated for the PP Population.

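### The log-rank test for time to first BM ignores the baseline BM rate already derived for every patient; on assumed inputs, adjusting for it adds about 0 to 10 points of power, and the overall contrast needs stratifying by age group

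*Combined protocol and SAP*

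**What the plan says.** SAP 5.2.4.3 covers each dose within an age group, the combined doses within an age group, and all active doses together. The distributions "will be estimated by the Kaplan-Meier method and will be compared by the Log-rank test". Protocol 8.8.2.3 plans the same ("estimated by the Kaplan-Meier method and will be compared by the Log-rank test"). Neither names a covariate, a stratum, a Cox model or an effect estimate. The output is medians, quartiles, curves and a p-value.

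The section just before it, SAP 5.2.4.2, models weekly BM rate with "fixed effects for gender (stratification variable), treatment, week, the interaction of treatment and week, and the corresponding baseline value". The covariate is defined there: "The baseline BM (and CSBM) rate will be calculated as the average BM (and CSBM) rate for each of the two weeks preceding initiation". SAP 3.3.7 gives the same derivation. SAP 3.2 states: "Central, block randomization will be performed with stratification by gender". SAP 3.3.1, Strata and Covariates, describes the enrolment and randomisation strata and adds no adjustment for this endpoint.

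**The concern.** Time to first BM and baseline BM rate both reflect a patient's bowel habit, so a patient with frequent BMs at baseline will probably have the next one sooner. When a strong predictor is left out of a survival comparison, the estimated treatment effect shrinks toward no difference and power falls. Each dose contrast has about 30 v 30 patients, so there is little power to spare. The sponsor also values the endpoint: protocol 3.3.1 discourages rescue use around Day 1 partly so that it can be measured accurately.

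Two further points follow from the same section. It plans no between-group estimate, whereas the mixed-model endpoints all get a difference with a 95% CI. And its overall contrast pools two age groups with different allocation ratios.

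**Working it through.** **1. The plan's own power figure.** The documents give power only for the primary endpoint. With 102 v 34 patients, a difference of 1.5 and SDs of 3.5 and 2.3: 1.5 / √(3.5²/102 + 2.3²/34) = 1.5 / 0.525 = 2.857, and Φ(2.857 − 1.960) = 81.5%. This reproduces the stated figure at two-sided alpha 0.05, but says nothing about time to first BM.

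**2. Benchmark for this endpoint.** Assume a hazard ratio (HR) of 1.75, an event in every patient and two-sided alpha 0.05. Schoenfeld power is Φ(√(D·p(1−p))·ln HR − 1.96), with D events and a proportion p on active drug.

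- 30 v 30: √15 × 0.560 = 2.17, power 58%
- 60 v 30: √20 × 0.560 = 2.50, power 71%
- 90 v 30: √22.5 × 0.560 = 2.65, power 76%
- 150 v 60: √42.9 × 0.560 = 3.66, power 96%

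**3. Effect of adjusting, first simulation.** Assumed: HR 1.75 given baseline, mean 3 BMs per week, hazard proportional to the patient's own rate except in the first row, baseline observed as a 2-week count, censoring at Day 28, and 1,500 trials per setting (Monte Carlo error about 1.3 points). CV is the coefficient of variation of patients' BM rates. Each cell gives power for plain log-rank → Cox with baseline → Cox with baseline, stratified by gender. Gender is not prognostic here.

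| Baseline | 30 v 30 | 60 v 30 | 90 v 30 |
|---|---|---|---|
| Not prognostic | 55 → 55 → 53% | 69 → 68 → 66% | 72 → 70 → 70% |
| CV 0.3 | 50 → 50 → 49% | 62 → 63 → 62% | 66 → 66 → 65% |
| CV 0.5 | 44 → 49 → 47% | 53 → 59 → 57% | 60 → 67 → 67% |
| CV 0.8 | 36 → 46 → 45% | 44 → 55 → 54% | 48 → 62 → 61% |

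Baseline alone changes power by −2 to +14 points, with the 14 at the widest assumed spread. Stratifying the log-rank test by gender alone changes it by −3 to +1 points, even with a gender HR of 1.5. Type I error was 4-7% for every method.

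**4. Effect of adjusting, second simulation.** Assumed: lognormal rates with mean 2.5 per week, no baseline week above 6, exponential times, censoring at Day 28, and 2,000 trials per setting. For SD of log rate 0.3, 0.5 and 0.7, the gains over the log-rank test were:

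- 30 v 30, HR 2.0: about 1, 3 and 8 points
- 90 v 30, HR 1.8: about 1, 6 and 8 points

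The mean correlation between log baseline rate and log time on placebo was about −0.11, −0.21 and −0.30. Null rejection was 5-6% for both tests.

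**5. Rescue.** The endpoint is first BM, not first SBM, and rescue is allowed after 72 hours without a BM. In the second model, about 37-46% of placebo patients reach 72 hours without one. With rescue-induced BMs added after that point, about 0 to 8 points of gain remain. In a run that assumed all these patients take rescue and have a BM within a day, log-rank power itself fell by 16-19 points at 90 v 30.

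**6. Overall contrast.** Group A is 60:30 and Group B is 90:30, so adolescents make up 90/150 = 60% of active patients but 30/60 = 50% of placebo patients. Power for 150 v 60 with treatment HR 1.5, where age HR compares adolescents with children (4,000 trials per setting):

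| Age HR | Plain log-rank | Stratified by age group |
|---|---|---|
| 0.67 | 62% | 73% |
| 1.0 | 74% | 73% |
| 1.5 | 78% | 72% |
| 2.0 | 80% | 72% |

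With no treatment effect, the mean plain statistic moved from −0.29 (age HR 0.67) to +0.39 (age HR 2.0). The stratified one stayed between −0.08 and −0.02.

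**The case against.** The strongest reply is that this is an optional efficiency choice on one unpowered secondary endpoint of a trial that calls itself exploratory, and that the log-rank test keeps its error rate. Within an age group that stands: nothing here makes the planned test invalid.

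The prognostic link is also assumed. Eligibility excludes patients with "> 6 SBMs per week for either week of the 2-week baseline diary assessment immediately preceding the randomization visit". That is a ceiling on SBMs, so a wide baseline spread cannot be inferred from it. If the spread is small, adjustment gains nothing. Rescue-induced BMs reduce the gain and make proportional hazards doubtful, a condition that the log-rank test does not need for validity. This stands, and it is why the log-rank test should stay as a supportive analysis.

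Three stronger readings are tempting, and the documents support none of them:

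- **Omitting gender costs power.** Gender stratification gained nothing and could cost up to about 3 points. Its only case is consistency with the randomisation and the other models.
- **A correlation of 0.5 would lift power from 60% to about 72%.** That applies the 1 − ρ² rule, which belongs to linear ANCOVA. The documents give no correlation, and the simulated ones did not exceed about 0.30 in size.
- **The SAP breaks its own convention.** Its models adjust for the corresponding baseline value, and time to first BM has none of its own. Rescue use (SAP 5.2.4.5) is also tested without adjustment.

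**Conclusion.** The point holds as a modest improvement. The planned test is valid within each age group but may give up power that data already collected could recover. A working range for the gain from baseline BM rate is about 0 to 10 points. It is near zero when the baseline spread is small, and only the widest spread at 90 v 30 exceeded the range clearly, at 14 points. The hazard ratios (1.75 to 2.0), mean rates (2.5 to 3 per week), spreads and Day 28 censoring are all assumptions.

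The overall contrast differs in kind. If age affects time to first BM, the unstratified test shifts with the age mix in either direction. Its higher power at an age HR above 1 is therefore partly an age difference, not treatment effect.

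**What to change.** Before unblinding, amend SAP 5.2.4.3 as follows:

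- Within each age group, test each contrast with a Cox model containing treatment and log(baseline weekly BM rate + 0.5), stratified by gender.
- For all active doses versus placebo, use the same model stratified by gender and age group.
- Report the hazard ratio with 95% CI for each contrast.
- Check proportional hazards, with attention to the period after 72 hours when rescue is allowed.
- Keep the Kaplan-Meier curves, medians and quartiles, and the log-rank test, as supportive results.

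The cost is SAP wording and at most eight models per analysis set (three contrasts in Group A, four in Group B, one overall). The downside is a hazard ratio that is conditional on baseline and relies on proportional hazards. If baseline proves unrelated to the endpoint, the full model with the gender stratum costs up to about 3 points of power in these simulations.
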